Mu wave suppression paradigm: If subjects agree to participate in this sub-study, the informed consent for EEG collection will be obtained prior to any EEG procedures. EEG waves will be recorded over 32-sites using a standard 32-electrode cap with the Biosemi system (9), while subjects are watching 60-80 second videos. The videos will consist of experimental conditions (point light animations of biological and non-biological motion, scrambled condition) and baseline condition (2 moving balls). All videos will be presented twice, using Presentation software (10). Data from both trials will be combined prior to analysis. Filters will be set to automatically identify and block any segments with eye movements and body movements (using +/- 40 microvolt deviations). Data will only be analyzed if there is at least 2 minutes of clean EEG per condition. For each segment, integrated power in the 8–13 Hz range will be computed using a Fast Fourier Transform. Mu suppression will be calculated for central (C3, Cz and C4) and occipital (O1 and O2) sites using the equation: Mu suppression = log10 (mu power of experimental condition/ mu power of ball condition). Occipital site electrical discharges will be recorded, integrated for power and compared between groups to determine if posterior alpha activity is causing differences across conditions.

STUDY PROCEDURES

Visit	Screen	Baseline	Midweek	3	4	5	6	7	8/ET
Week	-1	0	0	1	2	3	4	5	6
Days	-7 to -1	0	3/4	7	14	21	28	35	42
General Procedures									
Informed Consent	Х								
Assess Inclusion/Exclusion	Х	Х		Χ	Х	Х	Х	Х	Х
Medical History	Х								
Physical Exam	Х								
SCID/Psychiatric History	Х								
Urine Drug Screen ^b	Х								
Urine Pregnancy Screen ^c	Х	Х							
Vital signs/ weight	Х	Х		Χ	Χ	Х	Х	Х	Х
Blood chemistryd/Urine osmolality	Х								Х
Oxytocin Levels ^e		XX							Х
EEG	XX								Х

Clinician-Rated Scales									
PANSS ^f	(x)	Х		Х	Х	Х	Х	Х	Х
HAM-A/ CDSS/ CGI:S ⁹ /									
CGI:I/ GAF		Х		Х	Χ	Х	Х	Х	Х
Cognitive tests (CMINDS® and									Х
MSCEIT [™] ME) ^h	Х	Х							
Patient-Rated Scales									
CTQ	Х								
TSQM		Х		Х	Х	Х	Х	Х	Х
PTS/ SPIN/ ASEX ⁱ /									
ER-40/ ECR		XX		Х	Х	Х	Х	Χ	Х
Other Procedures									
Mid-Week Safety Call ^j			Х						
Dispense study drug		Х		Х	Х	Х	Х	Х	
Single Challenge Dose ^k	Х								
Concomitant Meds		Х	Х	Х	Х	Х	Х	Х	Х
Adverse Events		Х	Х	Х	Х	Х	Χ	Х	Χ
1-hr safety monitoring following in-									
clinic dose		Х							

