h Practice improvement is expected with repetition of some MATRICS tests. While the parallel group design will determine any improvement beyond the practice effect, neuropsychologists [name] and [name] have pointed out the majority of practice effect occurs between the first and second administrations of the MATRICS battery (personal communications). This finding by [name] and [name] regarding paper versions of the MATRICS™ should translate to the computerized versions of the CMINDS® as O'Halloran et al. (2007) found that standard paper administration versions and computerized administration versions of neurocognitive assessment instruments are substantially equivalent. These computerized versions yielded highly equivalent measures of absolute agreement throughout all the test batteries when compared to the standard paper versions. The group comparison will be between baseline (after the majority of practice effect has occurred) and 6 weeks. While this strategy may miss transient improvement between these timepoints it will decrease the practice effect. Transient improvements in cognition are not clinically meaningful.

All patient-rated scales except the ASEX will also be given 50 minutes after the in-clinic dose at the Baseline Visit.

^jA Mid-Week Safety Call to Study Site - The subject will be instructed to contact study staff on day 3 or day 4 of taking study drug. This call will be a brief open ended question and answer discussion to find out the subject's experiences with the study medication over the past few days and answer any questions that may arise.

^kA challenge dose will be administered between screening EEG paradigms. This dose will only be administered after all other inclusion/exclusion criteria have been verified. All subjects will receive 24IU as a challenge dose.

Study Procedure Details

Visit 1 – Screening (approximately 4-5 hours)

During Visit 1 of the study the volunteer will:

- Be asked questions about medical and psychiatric history
- Participate in a clinical interview called a Structured Clinical Interview for DSM-IV-TR (SCID) which is a structured question and answer discussion. This will be performed by a trained study staff who will ask a series of questions about behaviors and mood symptoms over time
- Be given a physical examination by one of the study doctors
- Have weight, pulse and blood pressure measured

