- If the volunteer is a woman capable of having children, a urine test will be done to ensure she is not pregnant
- Give a urine sample for testing to make sure there are no illegal or controlled substances in his/her body. The results of any urine drug screen will remain confidential and be disclosed only as required by law
- Blood draw (about one teaspoon or 5 mL) and urine sample will be collected that will include standard tests to make sure volunteers are healthy
- Be asked questions about health and any current illnesses or medications (including over-the-counter medications, herbal remedies, alcohol consumption, and substances of abuse).
 Be asked a series of questions about how s/he was feeling within the past few weeks such as whether there were anxious feelings, feelings of depression or difficulty concentrating. The volunteer will also possibly be asked about symptoms that are commonly associated with schizophrenia using a clinical interview called the SCI-PANSS (Structured Clinical Interview Positive and Negative Syndrome Scale).

The SCI-PANSS will be completed at the discretion of the investigator if he feels that the subject may not met entry criteria

- Complete a series of activities which will be used to measure process of thought called the CMINDS® and MSCEIT™ ME
- Premenopausal women will be queried regarding their menstrual cycles and data correlated with clinical findings
- Once all inclusion/exclusion criteria have been met subjects will have a baseline EEG performed
- Subsequently subjects will receive a, one time, challenge dose of 24 or 48 IU oxytocin followed by the EEG paradigm

Visit 2-Baseline (approximately 2 hours)

During Visit 2 – Baseline, the volunteer will:

- Have weight, pulse and blood pressure measured
- Be asked questions about health and any current illnesses or medications (including over-the-counter medications, herbal remedies, alcohol consumption, and substances of abuse)
- Be asked a series of questions about how s/he was feeling within the past few weeks such as whether
 there were anxious feelings, feelings of depression or difficulty concentrating. The volunteer will also be
 asked about symptoms that are commonly associated with schizophrenia using a clinical interview called
 the SCI-PANSS (Structured Clinical Interview Positive and Negative Syndrome Scale)
- Complete a series of activities which will be used to measure process of thought called the CMINDS® and MSCEIT™ ME

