- Complete a test on ability to recognize emotions called the Penn Emotion Recognition Test (ER-40) both pre and post in-office dose.
- Will be randomized to Group 1, 2, or 3 (described above) to receive either 84IU, 168IU of oxytocin or placebo
- Fill out questionnaires about mood at the time, experience with close relationships, and symptoms of paranoia both before and at least 50 minutes after the in-office dose of the study drug or placebo.
- Complete a questionnaire about sexual functioning
- The volunteer will be asked to stay at the clinic for one hour after taking the study drug so that the study doctor and study staff can monitor the first experience with the study drug. The study staff will ask questions about how the study drug affects the individual.
- When the study doctor decides the volunteer is ready to go, study drug will be dispensed along with written instructions on how and when to take the study drug.
- Have a blood and saliva sample taken at the beginning of the visit as well as 30 minutes after the in-office dose for monitoring of study drug levels within the body.

Mid-Week Call to Study Site (Day 3 or 4)

The volunteer will be instructed to contact study staff on day 3 or day 4 of taking study drug or the study staff will attempt to contact the volunteer. This information is also on the diary card. We will ask if the volunteer has had any unusual experiences since starting the study drug and if s/he has taken any medications other than the study drug and antipsychotic medication.

Visits 3-8 (weeks 1-6); (approximately 2-3 hours);

During Visits 3-8 of the study the volunteer will:

- Have weight, pulse and blood pressure measured
- Be asked questions about health and any current illnesses or medications (including over-the-counter medications, herbal remedies, alcohol consumption, and substances of abuse).
- Be asked a series of questions about how the volunteer is feeling within the past few weeks such as whether s/he has had anxious feelings, feelings of depression or difficulty concentrating. The staff will also

ask about symptoms that are commonly associated with schizophrenia using a clinical interview called the SCI-PANSS (Structured Clinical Interview – Positive and Negative Syndrome Scale)

- Study drug dispensed along with written instructions on how and when to take the study drug (except at Visit 8)
- Be asked a series of questions inquiring into any occurrences or events of note

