PANSS scores, duration of illness, class of medication) will be tested using treatment-by-baseline characteristic interaction terms in the MMRM LDA and/or ANCOVA models. To assess impact of improvement in one domain (e.g. positive symptoms) on the efficacy of a related symptom domain (e.g. negative symptoms), a mediator analysis model with terms for treatment, baseline, and positive symptoms improvement will be applied to determine significance of oxytocin effect on reductions in negative symptoms after adjustment for potential positive symptom improvement. We will perform similar mediator analysis for assessing inter-relationships between cognitive improvement and symptom improvement in positive and/or negative symptoms. In addition, cross-sectional baseline and longitudinal change score associations between treatment outcome measures and mediator effects will be assessed by including mediators as time-varying covariates in the MMRM LDA models (Diggle et al., 2001).

MU-Suppression. Data will be analyzed in two ways. Pearson rank correlations will be used to examine correlations between mu wave suppression in response to a single dose of OT and symptom severity at the end of 6 weeks of treatment. In additional exploratory analyses, mu suppression values will be split at the median into High suppressors and Low suppressors and followed up by correlations with symptom measures to determine if initial high suppression is correlated with greater improvement in symptom severity. Secondarily, Pearson rank correlations will be conducted between mu wave suppression and symptom severity at baseline, and between mu wave suppression and symptom severity after administration of a single dose of oxytocin.

Safety Endpoints. The safety dataset will contain all subjects who take at least one dose of oxytocin. All adverse events will be coded using the most current version of the Medical Dictionary for Regulatory Activities (MedDRA). The number and percentage of subjects reporting treatment-emergent adverse events will be tabulated within each dose group by treatment, system organ class (SOC) and MedDRA-preferred term. Treatment-emergent adverse events will be those adverse events that begin or worsened following the first dose of study drug. Adverse events will be further classified by severity and investigator-assigned relationship to study drug.

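### The open oxytocin challenge is given at Screening, but no adverse-event collection is scheduled until Baseline, and the safety definitions do not say whether the challenge counts as study drug

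*Combined protocol and SAP*

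**What the plan says.** All of the following is in Section 9 unless stated otherwise.

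- **Schedule of procedures.** The row "Single Challenge Dose" is marked in the Screen column only. The row "Adverse Events" is blank at Screen and marked at Baseline, the mid-week call and every later visit. The row beginning "1-hr safety monitoring following in" is marked at Baseline only.
- **Footnote k.** The challenge falls between the two screening EEG runs, and "All subjects will receive 24IU as a challenge dose".
- **Visit 1 text.** The list ends with a "challenge dose of 24 or 48 IU oxytocin followed by the EEG paradigm". No adverse-event question follows it.
- **Visit 2 text.** Subjects stay one hour after the in-clinic dose "so that the study doctor and study staff can monitor the first experience with the study drug".
- **Mu wave suppression paradigm.** The EEG work is optional: "If subjects agree to participate in this sub-study, the informed consent for EEG collection will be obtained prior to any EEG procedures".
- **Administration and dispensing.** The challenge is the one exception to double-blind dosing.
- **Safety Endpoints.** "Treatment-emergent adverse events will be those adverse events that begin or worsened following the first dose of study drug". The safety dataset is made up of subjects with one or more doses of oxytocin.
- **Analysis Methods.** The safety population is made up of subjects with one or more doses of study medication.
- **Section 15.** Adverse events are to be watched for over the whole study, subjects are to report them at once, and the investigator asks about the time since the previous visit.

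**The concern.** The first oxytocin a subject receives in this study comes at a visit where no adverse-event entry is scheduled. The one hour of planned observation comes at a later visit, and its stated reason is that the subject is meeting the drug for the first time. If footnote k is followed, that is not so.

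Two things are at stake. The first is the safety record: Specific Aim 5 asks whether daily intranasal oxytocin is safe and acceptable enough to develop further, and reactions to the one open dose belong in that picture. The second is attribution. Every challenged subject receives oxytocin before randomisation, including those later assigned to placebo. Unless the plan says where the challenge stands relative to study drug, the same event can be tabulated under a randomised arm or left out of the table, and the safety dataset can include or exclude the whole placebo arm.

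**Working it through.** The plan gives no figure of its own to reproduce here. The check is a comparison of passages and a count.

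**1. Schedule marks at the two visits**

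| Item | Screen | Baseline |
|---|---|---|
| Challenge dose | marked | blank |
| Adverse events | blank | marked |
| One-hour monitoring | blank | marked |

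Neither of the two safety items is marked at the visit where the challenge is given. The health question in the Visit 1 list comes before the challenge.

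**2. Delay to the first scheduled adverse-event entry.** The schedule puts Screening on days −7 to −1 and Baseline on day 0. The notes to the schedule allow both visits on one day. The longest delay is 0 − (−7) = 7 days and the shortest is 0 days. A challenged subject who does not return for Baseline has no scheduled entry.

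**3. Schedule against Section 15.** Section 15 commits to monitoring throughout but names no start visit and does not mention the challenge. It speaks of two baseline visits and of the start of each treatment period, whereas Section 4 describes one baseline visit and one six-week treatment phase. It therefore cannot be read as deliberately covering the challenge. The schedule and Section 15 do not agree.

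**4. Treatment-emergent events under two readings**

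| Event | Challenge counts as study drug | Challenge does not count |
|---|---|---|
| Starts after the challenge, over before Baseline | treatment-emergent, under the arm assigned later, placebo included | not treatment-emergent |
| Starts after the challenge, persists unchanged past Baseline | treatment-emergent | not treatment-emergent, provided the onset is recorded correctly |
| Starts after the challenge, worsens after the first randomised dose | treatment-emergent | treatment-emergent |

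The second row shows why a timely onset record matters, above all when Screening and Baseline fall on the same day.

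**5. Size of the oxytocin-based safety dataset.** Inputs: 24 on placebo and 48 on oxytocin (24 per dose), from Sample Size Calculation. Assume every randomised subject takes at least one randomised dose. Let *c* be the number of placebo subjects who took the challenge (0 to 24) and *u* the number challenged but never randomised, for which the documents give no figure.

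- Challenge does not count: 48, with no placebo subjects.
- Challenge counts: 48 + *c* + *u*. With all subjects challenged, *c* = 24, giving 48 + 24 = 72 randomised subjects, plus *u*.
- Challenge counts, but only sub-study volunteers take it: between 48 and 72, plus *u*. The placebo group is then limited to the volunteers.
- Analysis Methods population, with study medication meaning the randomised product: 24 + 48 = 72.

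The wording adds a further difficulty. Literally, the challenge is a dose of oxytocin, so it would bring subjects into the safety dataset even if it is not a dose of study drug for the treatment-emergent definition. Two sentences in one paragraph may thus start from different doses.

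**6. Who is challenged, and with what.** Footnote k says all subjects and 24 IU. The Mu wave suppression text makes the EEG work a sub-study with its own consent. The Visit 1 text gives 24 or 48 IU. These cannot all stand.

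**The case against.** The best reply is that the protocol leaves fewer gaps than the schedule suggests, and several stronger readings do fail.

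- **A reader might infer that challenge reactions go unrecorded.** The documents do not support that. Section 15 provides for general monitoring, immediate reporting and a question about the time since the last visit. The subject is still in clinic for the second EEG run. Baseline has an adverse-event entry at which an earlier onset can be noted. What stands is that none of this is scheduled at the challenge visit and that Section 15 does not clearly reach it.
- **A reader might infer that every subject is affected.** Footnote k says so, but the optional sub-study text does not.
- **A reader might infer that misattribution is built in.** The documents mostly use study drug for the randomised product: dispensing and the challenge are separate rows, and study drug is described as randomly assigned and then taken at Baseline. On that reading, treatment-emergent already starts at the first randomised dose. This is the likelier intention, but it is not stated, and the oxytocin-based safety dataset does not fit it. The challenge also precedes randomisation, so its after-effects should fall evenly on the arms in expectation. No systematic bias between arms follows.
- **A reader might extend the point to concomitant medication,** since that row is also blank at Screen. The Visit 1 text already asks about medications.
- **A reader might want a number of missed events.** The documents give no reaction rate for a single challenge. Section 14 says most studies reported no adverse effects and describes other effects as rare, mild and transient.

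It is also fair that Aim 5 concerns daily dosing, to which one challenge adds little.

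**Conclusion.** The point holds as a gap in scheduled collection together with undefined safety terms. Adverse-event collection is first scheduled 0 to 7 days after the open challenge, and never for a challenged subject who does not reach Baseline. This conflicts with the general commitment in Section 15. The oxytocin-based safety dataset has 72 randomised subjects or 48, depending on a question the plan leaves open, and at 48 there is no placebo arm to compare with. The two counts assume 24 per arm, all subjects challenged as footnote k says, and every randomised subject dosed. Totals of about 71 and of 80 also appear in the plan. They would shift the counts but not the contrast.

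No power, sample size or primary efficacy result is touched. The documents do not support a claim that reactions are lost, or any estimate of how many. The change is small and worth making.

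**What to change.** 1. Mark adverse-event recording in the Screen column at the challenge, and add a matching adverse-event question to the Visit 1 text after the dose.
2. List events between the challenge and the first randomised dose separately as pre-randomisation events, including those in subjects who are never randomised.
3. In Safety Endpoints, define treatment-emergent from the first randomised dose and say that the challenge is not study drug for this purpose.
4. Use one safety population for the arm comparison: subjects with at least one dose of randomised study medication, in line with Analysis Methods. Remove the oxytocin-based definition.
5. Reconcile the one-hour monitoring row and the Visit 2 reason for it with the earlier challenge. Reconcile footnote k with the optional sub-study text on who is challenged, and with the Visit 1 text on the dose. Align Section 15 with the visits this trial actually has. Which dose or observation arrangement is right is for the investigator and is not proposed here.

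The cost is one schedule mark, one case report form page, one listing and a few sentences of text.

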- To evaluate the safety of intranasal Oxytocin as measured by reported Adverse Events
- To evaluate the safety of intranasal Oxytocin as measured by collected safety measures to include blood tests, witnessed and reported adverse events
- To evaluate changes in ability to infer the mental state of others from emotion differentiation by their performance with the Penn Emotion Recognition Test (ER-40).
- To evaluate the possible correlation between the response to intranasal Oxytocin and biological markers, specifically endogenous oxytocin levels (tested via blood and saliva sample). Using saliva to test hormone levels has become a preferred method. Many hormone levels can fluctuate throughout the day. Using saliva allows for convenient specimen collection at multiple times (ie, pre and post dose). There is a believed correlation between the "bioavailable" (or active) amount of hormone in the blood and the levels found in saliva. We will collect both blood and saliva samples to confirm or reject the proposed correlation which may lead to a more convenient way of collection in future trials. Determining hormone bioavailability is critical with hormones and saliva as the specimen medium is ideal for this.
- To assess the differential effect of oxytocin on early environment and social parameters based on scores on the Childhood Trauma Questionnaire (CTQ) and Experience Close Relationships (ECR).
- To detect and monitor any changes in sexual functioning as rated by the Arizona Sexual Experience Scale (ASEX)
- To determine if expected deficits in neural processing of socially relevant visual stimuli (mu-rhythm suppression of mirror neurons) in schizophrenia patients correlates with the severity or nature of their symptoms
- To determine if intranasal oxytocin can improve mu rhythm suppression in schizophrenia patients

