^aScreening procedures can be done over a week period if needed to complete all procedures such as confirmation of diagnosis. The screening and baseline visits can occur on the same day.

^cPremenopausal women will be queried regarding their menstrual cycles and data correlated with clinical findings.Patients are instructed to use a medically accepted form of birth control through their study participation, and are also questioned about their birth control method at each visit. If a pregnancy is suspected at any time during the study, the patient will be asked to complete a urine pregnancy test.

^eOxytocin Levels will be collected via saliva and blood draw twice during the Baseline Visit. One blood draw and passive drool will be collected at the beginning of the visit (pre-dose) and a second blood draw and passive drool collection will be taken 30 minutes after the in-clinic dose. The third Oxytocin level will be taken at the patient's last visit (either Visit 8 at the conclusion of the protocol or the Early Termination visit).

^f PANSS must be done at baseline, but it may be completed at screening in addition at the discretion of the investigator if he feels that the subject may not met entry criteria

⁹The CGI-S will be completed twice at the Baseline Visit, once prior to dosing and a second time at least 50 minutes after the in-clinic dose of the study drug or placebo.

^b In addition to Visit 1, an optional urine drug screen or blood chemistry may be performed at any point during the study at the discretion of the Principal Investigator or study coordinators if it is suspected the subject is not abstaining from illegal substances or have general health concerns.

^d Basic Metabolic Panel includes Glucose, BUN, Creatinine, Bicarbonate, Chloride, Sodium, Potassium, Calcium, osmolality

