- Complete a questionnaire about symptoms of paranoia and sexual functioning
- Complete a test onability to recognize emotions called the Penn Emotion Recognition Test (ER-40).

Additionally at Visit 8 (week 6 or Early Termination);

- Complete a series of activities which will be used to measure process of thought called the CMINDS® and MSCEIT™ ME
- Have an additional blood sample taken (about 1 tablespoon) to monitor study drug levels in the blood
- EEG paradigm will be conducted

Follow Up Call

The volunteer will be asked to contact the study site one week after the last study drug dose to report taking any new medications or any unusual experiences since stopping the study drug.

Administration and dispensing of the study medication:

Except the one time challenge dose, this is a double-blind study, participants will be randomized to receive one of three possible intranasal study medications adjunctive to their antipsychotics: oxytocin 84 IU, oxytocin 168 IU or placebo (vehicle without oxytocin). Randomization will be performed stratifying gender groups, type of antipsychotic (typical versus atypical) and severity of symptoms based upon PANSS score (<90 versus >90) so that gender, symptom severity and antipsychotic type are distributed relatively evenly across treatment groups. Bottles containing placebo or two different concentrations of oxytocin will be formulated (See Study Drug Formulation below) so that the concentration of oxytocin in the high dose (168 IU) will be double that of the low dose (84 IU). All subjects will be instructed to spray 7 pumps of the spray bottle (one in each nostril, alternating nostrils) to achieve correct dose in the morning and again in the afternoon. Subjects will be given enough study drug at the time of the visit to last until the next visit with extra to cover approximately three additional days. Each pump bottle has 5 ml (300 IU) which is enough for 2.5 days of study drug. Therefore, subjects will be given one spray bottle supply at the time of each visit. The weight of each bottle will be recorded prior to dispensing. After all procedures are performed on baseline visit and study drug is randomly assigned, a dose of the study drug will be taken at the study site, in the presence of a staff member to insure correct administration.

Study Drug Compliance

- 1. Subjects will be instructed on proper use of the nasal device from study staff.

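### When screening and baseline share a day, the only oxytocin sample before randomized treatment can follow the active oxytocin challenge, so it may not measure the endogenous level

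*Combined protocol and SAP*

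**What the plan says.** **Visit timing.** Section 9, footnote a to the schedule: "The screening and baseline visits can occur on the same day". The schedule itself puts screening on Days -7 to -1 and baseline on Day 0, and section 4 describes a 7-day screening period followed by a baseline visit.

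**Challenge.** The schedule marks a single challenge dose in the screening column. Footnote k places it between two EEG recordings and says "All subjects will receive 24IU as a challenge dose", once every other entry criterion has been checked. The Visit 1 text ends with: "Subsequently subjects will receive a, one time, challenge dose of 24 or 48 IU oxytocin followed by the EEG paradigm". The challenge is active drug and is outside the blind: "Except the one time challenge dose, this is a double-blind study".

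**Samples.** Footnote e says of the baseline visit: "One blood draw and passive drool will be collected at the beginning of the visit (pre-dose"), and then "a second blood draw and passive drool collection will be taken 30 minutes after the in-clinic dose". The schedule shows one further sample, at the final visit.

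**Use.** A secondary objective in section 6 relates response to biological markers, "specifically endogenous oxytocin levels (tested via blood and saliva sample"). The Statistical Consideration part of section 9 describes no analysis of these levels and does not name the sample to be used.

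**Ratings.** Footnote f says "PANSS must be done at baseline" and leaves a screening PANSS to the investigator's discretion. CGI-S, the patient scales, ER-40 and the cognitive battery are also scheduled at baseline.

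**The concern.** The first sample is pre-dose only in relation to the randomized in-clinic dose. On a same-day schedule it comes after the challenge, so it may contain exogenous oxytocin. Subjects seen on separate days would contribute a cleaner value, and the analysis would pool the two kinds without distinguishing them.

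The endogenous level enters as a subject-level marker correlated across subjects with response. If same-day scheduling is unrelated to response, contamination weakens a true correlation. If the two are related, for instance because certain kinds of patient tend to be scheduled on one day, it could produce a spurious one. Neither can be repaired afterwards, because no other sample precedes randomized treatment, and the documents do not provide for recording the time of the challenge.

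**Working it through.** The plan states no figure to reproduce. The check is whether the sequence can occur as written, and how short the gap can be.

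1. **Is one day feasible?** Visit 1 is listed at about 4-5 hours and Visit 2 at about 2 hours. 4 + 2 = 6 and 5 + 2 = 7, so 6-7 hours in all. It is feasible, and footnote a permits it.

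2. **What lies between the challenge and the first sample?** Only the post-challenge EEG remains in Visit 1. The mu-suppression paragraph lists three experimental conditions plus the ball condition, each shown twice, with videos of 60-80 seconds. Assuming one video per condition:
   - 4 × 2 × 60 s = 480 s = 8 min
   - 4 × 2 × 80 s = 640 s = 10.7 min

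   Set-up and any wait between dose and recording are not stated. The gap could therefore be well under an hour, or several hours.

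3. **How does that compare with the plan's own timings?** The plan samples 30 minutes after the in-clinic dose to see drug levels. It repeats CGI-S and most patient scales about 50 minutes after that dose. A sample taken soon after the challenge falls in the period in which the plan expects to see drug.

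4. **How large is the challenge relative to one in-clinic dose (42 or 84 IU)?**
   - 24/42 = 57%; 24/84 = 29%
   - 48/42 = 114%; 48/84 = 57%

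   Footnote k and the Visit 1 text disagree on the challenge amount. On either reading it is not trivial beside a study dose.

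5. **Does anything prevent the sequence?** No section sets a minimum interval, requires the sample before the challenge, or bars challenged subjects from a same-day baseline. Footnote k's condition concerns entry criteria, and oxytocin level is not one of them.

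6. **Can the effect be sized?** Let p be the share of samples contaminated and g the shift in SDs of the true level. The share of variance that is artefact is p(1-p)g² / [1 + p(1-p)g²]. Both inputs are assumptions:
   - g = 0: 0%
   - p = 0.10, g = 0.5: 0.0225/1.0225 = 2%
   - p = 0.25, g = 1: 0.1875/1.1875 = 16%
   - p = 0.50, g = 2: 1/2 = 50%

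   The result runs from nothing to half, depending only on what is assumed. The documents do not narrow it.

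**The case against.** **The ratings may be protected.** Footnote k requires all other entry criteria to be verified before the challenge. Section 10 sets PANSS total of at least 55 and CGI-S of at least 4, both at baseline. Read literally, those two ratings come before the challenge. A reader might infer that the baseline PANSS, and so the primary endpoint, is contaminated; the documents do not support that. What remains is an ordering conflict, because footnote k's condition does not fit the listed visit order or an optional screening PANSS. The condition does not cover the oxytocin samples, the cognitive battery or the patient scales.

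**Symptoms may not move after one dose.** Section 6 reports that in the earlier study, at 80 IU, benefit appeared only at three weeks. This is a fair argument against a shift in symptom ratings. It says nothing about measured hormone levels.

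**Randomization balances it.** The challenge precedes randomization. No systematic bias is therefore expected in the primary comparison, or in between-arm comparisons of change around the first dose. This stands in full. It does not help the endogenous-level correlation, which needs each subject's own uncontaminated value.

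**Few subjects may be exposed.** Section 9 makes the EEG a sub-study that subjects may decline, section 20 allows for a separate EEG visit, and the default schedule separates screening from baseline. A reader might take every subject, or every same-day subject, to be affected. That does not follow: footnote k says all subjects are challenged, the sub-study wording suggests only some, and the share seen on one day is not given.

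**Conclusion.** The point holds for the oxytocin sample. As written, a challenged subject with same-day visits can have the only sample before randomized treatment taken after exogenous oxytocin, possibly within an hour. That threatens the secondary correlation of endogenous level with response. Same-day baseline cognition and pre-dose patient scales may also be affected, but the documents do not show that they are.

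This rests on two readings: that the pre-dose baseline sample is the endogenous measure, since no other sample precedes randomized treatment, and that the visit procedures run in the order listed. The number of subjects and the size of any carry-over are unknown, so none of the percentages in the working should be taken as an estimate. The matter is confined to one secondary objective, and possibly some secondary baseline measures, of a pilot study. It is still worth correcting now, because the remedy is cheap and the sample cannot be retaken.

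**What to change.** 1. When both visits fall on one day, collect the endogenous blood and saliva sample before the challenge.
2. Record the clock times of the challenge and of every oxytocin sample.
3. State in the analysis plan which sample is the endogenous level, and exclude from that analysis any sample taken after a same-day challenge.
4. Reconcile footnote a with the Days -7 to -1 and Day 0 schedule; footnote k's statement that all subjects are challenged with the sub-study wording; footnote k's condition on entry criteria with the visit order and the optional screening PANSS; and the two statements of the challenge amount. The order of the challenge and the baseline ratings should then read the same throughout. Which version governs is for the investigators to settle.

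Moving all baseline ratings ahead of the challenge for every subject is not suggested. With the challenge at screening, it would cut across footnote f and across footnote h's plan to use the second cognitive administration as the baseline.

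The cost is a sampling-order rule, time fields, slightly less scheduling freedom and perhaps a few excluded samples. On same-day visits the first sample would no longer sit immediately before the in-clinic dose, so those subjects should be flagged when the first sample is compared with the 30-minute sample.
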